#### 6.11.2 SBP and DBP from office visits BP

Vital signs will be measured as indicated in the Schedule of Events ([Appendix 1](#)) and will include pulse, sitting, supine, and standing BP. Vitals should be measured prior to blood draws following the procedures described in Section 6.7.

#### 6.11.3 Body weight

The body weight must be determined using a scale that is calibrated. The same scale should be used throughout the study duration.

#### 6.11.4 Pulse Pressure

The pulse pressure will be calculated as the difference between mean systolic and diastolic BP of the ABPM.

#### 6.11.5 Trough/Peak Ratio

Trough/Peak ratio will be calculated based on the four valid measurements centered on approximate  $T_{max}$  (4 h post-dose) and the four valid measurements immediately preceding the removal of the monitor and prior to administering a tablet.

### 6.12 Adverse Events Assessments

#### 6.12.1 Definition of Adverse Events

**Adverse event (AE):** Any untoward medical occurrence in a subject administered a pharmaceutical product that does not necessarily have a causal relationship with the treatment.

An AE can therefore be any unfavorable and unintended sign (including an abnormal laboratory finding), symptom, or disease temporally associated with the use of a medicinal product, whether or not it is considered related to the medicinal product use.

**Serious adverse event (SAE):** A serious AE (SAE) or reaction is any untoward medical occurrence that at any dose:

- results in death
- is life-threatening (NOTE: The term "life-threatening" in this context refers to an event in which the subject was at risk of death at the time of the event; it does not refer to an event which hypothetically might have caused death if it were more severe)
- requires inpatient hospitalization or prolongation of existing hospitalization
- results in persistent or significant disability/incapacity
- is a congenital anomaly/birth defect
- is a medically important event or reaction. Medical and scientific judgment should be exercised in deciding whether a situation should be considered serious. Important medical events which jeopardize the subject or require intervention to prevent one of the outcomes listed above should usually be considered serious. Examples of such events are intensive treatment in an emergency room or at home for allergic bronchospasm; blood dyscrasias or convulsions that do not result in hospitalization; or development of drug dependency or drug abuse

**Adverse Reaction:** An adverse reaction means any AE caused by a drug. Adverse reactions are a subset of all suspected AEs in which there is a reason to conclude that the drug caused the event.

**Expectedness:**

- Defines any adverse events that are expected, based on the Investigator Brochure and previous clinical trials.
- Describe the means for determining and reporting unexpected adverse events.

**Unexpected Adverse Drug Reaction (UADR):** An adverse reaction, the nature or severity of which is not consistent with the applicable product information (e.g. Investigator's Brochure for an unapproved investigational medicinal product).

**Serious and Unexpected Suspected Adverse Reaction (SUSAR):** A serious UADR. The sponsor must report any suspected SUSAR in an IND safety report (21 CFR 312.32(c)(1)(i)). Before submitting an IND safety report, the sponsor needs to ensure that the event meets all three of the definitions:

- Suspected adverse reaction
- Serious
- Unexpected

**Severity:** AEs will be graded on a 3-point scale and reported as indicated in the CRF. The intensity of an AE is defined as follows:

- 1 = Mild: event is medically significant but produces no disruption to daily activity
- 2 = Moderate: event is medically significant and reduces or affects normal daily activity
- 3 = Severe: event is medically significant and results in inability to work or perform normal daily activity

**Investigational Product Causality:** An assignment made by the investigator based on the circumstances of the event and its analysis. Cases with causal relationship classified as possible, probable, or definite are defined as related. Cases with causal relationship categorized as not likely or unrelated are defined as not related. Relationship of an AE to dosing will be assessed as follows:

- **Definite:** The event responds to withdrawal of the investigational product (dechallenge), and recurs with rechallenge by administration of the investigational product
- **Probable:** There is a reasonable causal relationship between the investigational product and the AE. The event responds to dechallenge. Rechallenge is not required
- **Possible:** There is a reasonable causal relationship between the investigational product and the AE. Dechallenge is lacking or dechallenge response is unclear
- **Not Likely:** There is a temporal relationship to investigational product administration, but there is not a reasonable causal relationship between the investigational product and the event
- **Unrelated:** There is not a temporal or causal relationship to investigational product administration

#### 6.12.2 Eliciting and Reporting AEs

After a subject consents to participation in the study, the investigator will periodically assess subjects for the occurrence of AEs. To avoid bias in collecting information about AEs, the investigator should ask subjects the following question: "How have you felt since you were last checked?" All AEs (serious and non-serious) reported by the subject must be recorded in the source documents and CRFs.

It is the investigator's responsibility to review the results of all laboratory tests as they become available. For each abnormal laboratory test result, the investigator needs to ascertain if this is a clinically significant change from baseline for that individual subject. This determination, however, does not necessarily need to be made the first time an abnormal value is observed. The investigator may repeat the laboratory test or request additional tests to verify the results of the original laboratory tests. If the laboratory value is determined to be a clinically significant and abnormal change from baseline for that subject, this is considered a laboratory AE.

In addition, the sponsor's Medical Monitor or its designated personnel must be notified immediately by telephone, email, or fax of any immediately reportable AEs (IRAE) according to the procedure outlined below. Special attention should be paid to recording hospitalization and concomitant medications.

#### 6.12.3 Immediately Reportable AEs

The investigator must report any SAE to the sponsor or its representative immediately after the investigator becomes aware of the event. An SAE form should be completed and sent to the sponsor or its representative within 24 hours of knowledge of the event.

Non-serious events that require discontinuation of investigational product (including laboratory abnormalities) should be reported to the sponsor within 3 working days. The CRF AE form should be completed as directed by to the sponsor.

Subjects experiencing an SAE should be followed clinically until their health has returned to baseline status or no further improvement in condition can be expected with further care. It is expected that the investigator will provide or arrange appropriate supportive care for the subject.

#### 6.12.4 Pregnancy

Women of childbearing potential (WOCBP) are defined as any female who has experienced menarche and who is not permanently sterile or postmenopausal. Postmenopausal is defined as 12 consecutive months with no menses without an alternative medical cause. WOCBP who are sexually active must use an effective method of birth control during the course of the study, in a manner such that risk of failure is minimized.

Before enrolling WOCBP in this clinical trial, investigators must review guidelines about study participation for WOCBP. The topics should generally include:

- General information
- Informed consent form
- Pregnancy prevention information
- Drug interactions with hormonal contraceptives
- Contraceptives in current use
- Guidelines for the follow-up of a reported pregnancy

Prior to study enrollment, WOCBP must be advised of the importance of avoiding pregnancy during trial participation and the potential risk factors for an unintentional pregnancy. The subject must sign an informed consent form confirming that the above-mentioned risk factors and that the consequences were discussed with her.

During the study, all WOCBP should be instructed to contact the investigator immediately if they suspect they might be pregnant (e.g. missed or late menstrual cycle).

If a subject or investigator suspects that the subject may be pregnant prior to investigational product administration, the investigational product administration must be withheld until the results of serum pregnancy tests are available. If the pregnancy is confirmed, the subject must not receive the investigational product and must not be enrolled or remain in the study. If pregnancy is suspected while the subject is receiving study treatment, the investigational product must be withheld immediately until the result of the pregnancy test is known. If pregnancy is confirmed, the investigational product will be permanently discontinued and the subject will be withdrawn from the trial. Exceptions to study discontinuation may be considered for life-threatening conditions only after consultations with a sponsor Medical Monitor or designated personnel. The investigator must notify the Medical Monitor within 3 working days of any female subject who becomes pregnant. This reporting requirement will continue until 4 weeks after the last investigational product exposure.

The investigator must record the event on the Pregnancy Surveillance Form and forward it to sponsor's Medical Monitor.

Protocol required procedures for study discontinuation and follow-up must be performed on the subject unless contraindicated by pregnancy (e.g. x-ray studies). Other appropriate pregnancy follow-up procedures should be considered if indicated. In addition, the investigator must report to the sponsor, on the appropriate Pregnancy Surveillance Form, follow-up information regarding the course of the pregnancy, including perinatal and neonatal outcome. Infants will be followed for a minimum of six months.

#### 6.12.5 Procedure for Breaking the Blind

As indicated in [Section 5.5](#) above, the sponsor, medical monitor, study coordinators, pharmacists, study subjects, and the CEC members will be blinded to the treatment assignment during the study. The investigator should also remain blinded to the subject treatment during the entire study unless knowledge of the subject's treatment is required for clinical care and safety. The Emergency Code Break module in the IWRS is used for such situations. The investigator must confirm the intention to unblind the subject's treatment to obtain the dose information in IWRS. Upon completion of the unblinding, the system will send an alert to designated study team members that an unblinding event has occurred. Documentation of breaking the blind should be recorded in the subject's medical record with the date and time the blind was broken, and the names of the personnel requesting and authorizing unblinding. The treatment assignment will continue to be withheld from the CEC members.

#### 6.12.6 Follow-up of Non-Serious AEs

Non-serious AEs that are identified on the last scheduled contact must be recorded in the AE CRF with the current status noted. All non-serious events that are ongoing at the time will be recorded as ongoing in the CRF.

#### 6.12.7 Follow-up of Post-Study SAEs

SAEs that are identified on the last scheduled contact must be recorded on the AE CRF page and reported to the sponsor according to the reporting procedures outlined in [Section 6.12.3](#). These may include unresolved previously reported SAEs, or new SAEs. The investigator should follow these SAEs until the events are resolved, or the subject is lost to follow-up. Resolution means the subject has returned to the baseline state of health, or the investigator does not expect any further improvement or worsening of the subject's condition. The investigator should continue to report any significant follow-up information to the sponsor until the event has been resolved.

Any new SAEs reported by the subject to the investigator that occur after the last scheduled contact, and are determined by the investigator to be reasonably associated with the use of the investigational product, should be reported to the sponsor or designated personnel. This may include SAEs that are captured on follow-up telephone contact or at any other time point after the defined study period (i.e. up to last scheduled contact). The investigator should

follow SAEs identified after the last scheduled contact until the events are resolved, or the subject is lost to follow-up. The investigator should continue to report any significant follow-up information to the sponsor until the event has been resolved. This study requires that subjects be actively monitored for SAEs for at least 4 weeks after the last treatment.

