## **6.11 Efficacy Assessments**

### **6.11.1 24-h ABPM**

ABPM will be performed for 24 hours, with measurements every 15 minutes during the day (16 h) and every 30 minutes during the night (8 h). Subjects will be fitted with the ABPM device, administer one tablet of study drug, and wear the cuff for 24 consecutive hours at the specified visit ([Appendix 1](#)). Subjects should take the study drugs while taking all their normal medications and performing normal daily activities. Subjects will be instructed to refrain from strenuous exercise or shower during this period. The ABPM device will be

placed on the arm by study staff and begin recording values immediately following the dosing.

If the ABPM is not completed or if < 64 BP readings (51 day time and 13 night time BP readings) are recorded, the procedure must be repeated. A new bottle of double blind study drug can be dispensed to a subject only after the 24 h ABPM is completed successfully.

Prior to randomization, subject who cannot complete the 24h ABPM within two attempts will be considered a screen fail. After randomization, if a subject cannot complete a 24h ABPM within two attempts, the data will be considered missing.

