### **7.11 Visit 11 (Cumulative Week 36 + 1 Day)**

- Measure vital signs, including BPs and heart rate
- End 24-h ABPM and download readings. The 24-h ABPM should be repeated within 2 days if <64 BP readings (51 day time and 13 night time BP readings) are recorded successfully
- Assess AEs
- Record concomitant medications

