3.10. STUDY PROCEDURES AND FLOWCHART

The activities that must be performed at each clinic visit listed below are presented in Table 1.

A visit window of ± 3 days is allowed for all post-randomization visits. Visit 3 is the day of randomization and the basis for the visit window. A repeat ABPM shall be performed within 2 days if the 24h-ABPM is incomplete. Only the second set of ABPM data will be entered in the case report form on visits 2-3, 5-6, 8-9, and 10-11. The other specified procedures in the same assessment period do not need to be repeated. If the ABPM fails twice at visit 3 prior to randomization, the subject is considered a screen failed subject. If the ABPM cannot be completed successfully twice after randomization, the ABPM BP for that assessment period is considered missing.

Procedures listed for visit 10 and 11 will be completed if a subject is withdrawn from the study.

Table 1 Schedule of Events

Procedures	Screening/ Run-in		Study 603A			Study 603B					
			Weeks 1 to 12			Weeks 1 to 12			Week 13 to 24		
Cumulative study week			1-12			13-24			25-36		
Visit Number	1	2	3	4	5	6	7	8	9	10	11
Time to first randomization	-13 or -12 d	-1d	0w +1d	6w	12w	12w +1d	18w	24w	24w +1d	36w	36w +1d
Informed Consent	x										
Medical History	x										
Inclusion/Exclusion Criteria	x	x	x								
Run-in drug dispensation	x										
Randomization			x						x		
Begin 24-h ABPM		x			x			x		x	
End 24-h ABPM			x			x			x		x
Double blind drug dispensation			x			x			x		
Whole blood sample	x	x			x			x		x	
Hematology	x	x			x			x		x	
HbA1c	x	x			x			x			
Serum sample										x	
Chemistry	x	x			x			x		x	
Lipids	x	x			x			x		x	
Urine sample											
Urinalysis	x	x			x			x		x	
Pregnancy test (WCBP)	x	x			x			x		x	
Population PK Sampling							x	x			
12-Lead ECG	x	x			x			x		x	
Vital Signs	x	x	x	x	x	x	x	x	x	x	x
Abbreviated PE & weight	x				x			x		x	
Complete PE & weight		x									
Adverse Events Assessments		x		x	x		x	x		x	x
Concomitant Medication Assessments		x		x	x		x	x		x	x

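### Four weeks of active SAE monitoring after the last treatment are required, but the last scheduled contact is about one day after the last tablet

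*Protocol*

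**What the plan says.** The requirement closes Protocol 6.12.7: "This study requires that subjects be actively monitored for SAEs for at least 4 weeks after the last treatment". The same section sets the rule for new SAEs after the last scheduled contact. They are to be passed on if the subject reports them "and are determined by the investigator to be reasonably associated with the use of the investigational product". It adds: "This may include SAEs that are captured on follow-up telephone contact or at any other time point after the defined study period", and it treats the defined study period as ending at the last scheduled contact.

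Protocol 6.12.3 is broader and has no causality condition: "The investigator must report any SAE to the sponsor or its representative immediately after the investigator becomes aware of the event".

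The schedule in Protocol section 7, Appendix 1 and SAP Table 1 ends at Visit 11, cumulative week 36 + 1 day. The final ABPM starts at Visit 10, where under Protocol 6.11.1 the subject is to "administer one tablet of study drug, and wear the cuff for 24 consecutive hours at the specified visit". Study drug is dispensed only at Visits 3, 6 and 9 (Protocol 5.4). Protocol 3.3 gives total participation as 38 weeks.

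For subjects who leave early, SAP 3.10 says: "Procedures listed for visit 10 and 11 will be completed if a subject is withdrawn from the study". The introduction to Protocol section 7 names Visit 10 only. SAP 3.10 also states: "A visit window of ± 3 days is allowed for all post-randomization visits".

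SAP 9.3 ends AE collection at the last scheduled contact. It brings later SAEs into the analysis only under the same relatedness condition as 6.12.7.

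**The concern.** The 6.12.7 sentence is mandatory: it applies to all subjects and calls for active monitoring over a fixed minimum period. Active monitoring means that someone asks. Yet a site could complete every scheduled procedure without asking any subject about SAEs after the day following the last tablet. What remains is passive capture: the subject has to volunteer the event, and the investigator has to judge it related.

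Two things are at stake. First, a study report claiming four weeks of active SAE monitoring would have no support in the schedule. Second, a serious event judged unrelated is named neither in the post-contact reporting rule nor in the SAP's analysis rule, although 6.12.3 would still require it to be reported if the site heard of it. Sites are left to reconcile 6.12.3 with 6.12.7 themselves, so practice may differ between them.

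**Working it through.** **1. The plan's own duration.** With Visit 1 at Day -13, 36 weeks of treatment and Visit 11 one day later:

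- 13 + 36 × 7 + 1 = 266 days, and 266 / 7 = 38.0 weeks.
- With Visit 1 at Day -12: 265 / 7 = 37.9 weeks.

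This reproduces the 38 weeks in Protocol 3.3, so that total contains no follow-up period. With four weeks of follow-up it would be 2 + 36 + 4 = 42 weeks.

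**2. Days with no scheduled contact.** The required period is 28 days.

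- On schedule, the last tablet is at Visit 10 and the last contact one day later: 28 - 1 = 27 days.
- If a failed ABPM is repeated within 2 days, the last contact is about 3 days after Visit 10: 28 - 3 = 25 days. This assumes no further tablet at the refitting. If one is taken, the gap returns to about 27 days.
- At the arithmetic extreme of the ±3-day windows, Visit 10 is 3 days early and Visit 11 is 3 days late: 3 + 1 + 3 = 7 days apart, and 28 - 7 = 21 days.
- A subject who stopped the drug before the final or exit visit has a shorter gap, depending on when the last tablet was taken.

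**3. Subjects (sample size sections of both documents).**

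- Expected completers of 36 weeks: 680 × 0.75 = 510.
- Expected early leavers: 680 - 510 = 170.
- Completers ending on bexagliflozin after 1:1 re-randomization, assuming equal completion in both arms: 510 / 2 = 255.

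**4. Person-time in the window, completers ending on bexagliflozin.**

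- 255 × 27 / 365.25 = 18.9 patient-years.
- 255 × 21 / 365.25 = 14.7 patient-years.

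**5. SAEs expected to occur in that time.** The documents give no SAE rate. I assume 3 to 10 per 100 patient-years.

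- 27 days: 18.9 × 0.03 = 0.6 to 18.9 × 0.10 = 1.9.
- 21 days: 14.7 × 0.03 = 0.4 to 14.7 × 0.10 = 1.5.

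For all 510 completers, whichever treatment they ended on: 510 × 27 / 365.25 = 37.7 patient-years, or 1.1 to 3.8 SAEs at the same rates. These are events occurring, not events missed.

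**6. Provisions that might supply the monitoring.**

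- Telephone contact (6.12.7) is named only as a possible source of reports. It has no date, and no call appears in any schedule.
- Immediate reporting (6.12.3) applies once the investigator is aware of an event and requires nobody to enquire.
- MACE follow-up (6.12.9) lasts for the duration of the study and covers MACE only.
- SAP 9.3 has the same end point and the same relatedness condition as 6.12.7. Its combined-period TEAE summary also stops at the last bexagliflozin dose.

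None of these provides a scheduled enquiry within the four weeks.

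**The case against.** The strongest reply is that the duty already exists. The sentence in 6.12.7 binds sites, the paragraph names telephone contact as a route, and a visit table without a telephone row does not cancel the text. On this view only the date and method are missing, and operational documents not available here may supply them. That is fair as far as it goes. But the protocol neither schedules nor requires a call, and the SAP's analysis rule is a relatedness filter, so the gap is more than missing detail.

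A second reply is that a specific post-study rule can stand beside the general rule in 6.12.3 without contradicting it. That is reasonable. The two are in tension rather than in flat conflict, and collecting all SAEs to day 28 is a recommendation that 6.12.7 does not itself spell out.

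Three points on the numbers stand in part:

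- The 21-day figure is an extreme, because Visit 11 ends the 24-hour recording begun at Visit 10. The realistic range on schedule is 25 to 27 days.
- The SAE rate is assumed.
- The protocol lists Visit 10 only for withdrawn subjects. Without Visit 11 the gap could be slightly longer than the SAP wording implies.

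None of these removes the mismatch. It is also true that the consequences are modest.

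**Conclusion.** The concern holds. The plan promises a safety property that its schedule and analysis rule do not deliver. For a subject who finishes on schedule, about 27 of the 28 days lack any scheduled contact. For the roughly 170 expected early leavers the gap is up to about 27 days under the SAP's exit procedures, and less if the last tablet came before the exit visit.

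The expected number of events is small and rests on the plan's 75% completion estimate, equal completion by arm and an SAE rate the documents do not give. The rule is the same in both blinded arms, so no between-arm bias is shown. The primary analyses, their power and Type I error are untouched. The change should be made because the requirement is explicit and the cure is cheap, not because a large effect is expected.

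**What to change.** 1. Add a telephone safety contact at last dose + 28 days to Protocol section 7, Appendix 1 and SAP Table 1, and change the duration in Protocol 3.3 to about 42 weeks. Make the same call to withdrawn subjects unless a later contact already covers day 28.
2. In 6.12.7 and SAP 9.3, collect and report all SAEs up to day 28 regardless of causality, in line with 6.12.3. Keep the relatedness filter only after day 28. Because SAP 9.3 ties AE collection to the last scheduled contact, state whether non-serious AE collection still ends at Visit 11.
3. Show these SAEs in the existing serious-AE listing (SAP 9.3.2) by last treatment. No new table is needed.
4. If the call cannot be added, or cannot reach subjects who have already finished, remove or qualify the four-week sentence.

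The cost is at most 510 + 170 = 680 calls, a protocol amendment with IRB/IEC approval, and SAP wording. No visit or sample is added. SAP section 10 reports the interim analysis as already done, so some subjects may finish before an amendment takes effect. Their number is not given. SAE ascertainment would then be mixed, and the report would have to say so.
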